Title: Treatment of Pressure Ulcers using Biological Skin Substitutes: A Comparison of Type-I Collagen and Amnion/Chorion Membranes

NCT: NCT06853210

Date: 26/07/2025

Background

Pressure ulcers, also known as decubitus ulcers or bedsores, are localized injuries to the skin and underlying tissue resulting from prolonged pressure. They are prevalent in individuals with limited mobility, such as the elderly and those with spinal cord injuries, particularly in long-term care settings. Effective management of pressure ulcers is crucial to prevent complications and improve patient outcomes, includes pressure relief, wound care, and advanced therapies such as bioengineered skin substitutes. Management of pressure sores is crucial due to their association with increased morbidity, healthcare costs, and reduced quality of life. This study aims to evaluate the efficacy of two treatment modalities: Type-I Collagen-based Skin Substitute (HPTC) vs. Dehydrated Human Amnion/Chorion Membrane (dHCAM) in promoting the healing of pressure ulcers. While both products are used in wound management, direct comparative studies evaluating their efficacy in treating pressure ulcers are limited.

MATERIALS AND METHODS

This prospective, randomized, controlled, open label, two parallel group, single-centre clinical trial will be conducted at a tertiary care hospital, in India, specializing in wound care and reconstructive surgery. The study protocol was approved by the Institutional Ethics Committee (Approval Number: AIMS/IEC/012/2025) and pre-registered with the ClinicalTrials.gov (NCT06853210). All procedures will be performed in accordance with the Declaration of Helsinki and Good Clinical Practice guidelines. All participants or guardians will be provided informed consent.

Outcome Measures

Primary Outcome:

- a. Percentage Wound Area Reduction.
- b. Histopathological Parameters
 - i. Vascular Infiltration
 - ii. Neo-epithelialization
 - iii. Fibroblast Activity
 - iv. Capillary Density
 - v. Inflammatory Response
 - vi. Collagen Deposition

Secondary Outcomes:

- a. Complete Wound Closure Rates (defined as 100% epithelialization).
- b. Wound Size Progression Over Time 7 weeks

- c. Number of Reapplications
- d. Incidence of treatment-related adverse events (e.g., infection, allergic reactions)
- e. Quality of Life Improvement
- f. Patient Satisfaction Scores

Study Design

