Prospective, randomized, controlled, single-centre study with two parallel-group, open-label trial Duration: 6 weeks of intervention with follow-up for 1 week. Participants will be randomly assigned in a 1:1 ratio to receive either HPTC or dHCAM treatment

Sample Size: 80 patients (40 per arm)

- i. Group A: 20 patients receiving HPTC treatment.
- ii. Group B: 20 patients receiving dHCAM treatment.

Eligibility Criteria

Inclusion criteria

- a. Subjects must be at least 18 years of age or older
- b. Presence of a Stage III or Stage IV pressure ulcer, as defined by the National Pressure Ulcer Advisory Panel
- c. Ulcer size between 5 cm² and 25 cm²
- d. Ulcer duration of at least 4 weeks prior to enrolment
- e. The subject must agree to attend the twice-weekly/weekly study visits required by the protocol
- f. The subject must be willing and able to participate in the informed consent process
- g. Adequate blood supply to the affected area, confirmed by clinical assessment

Exclusion criteria

Potential subjects meeting any of the following criteria will be excluded from enrolment.

- a. A subject known to have a life expectancy of <6 months
- b. Presence of infection in the ulcer requiring systemic antibiotics.
- c. Known allergy to components of HPTC or dHCAM.
- d. Participation in another wound care study within the last 30 days.
- e. A subject with autoimmune or connective tissue disorders.
- f. Women who are pregnant or considering becoming pregnant within the next 6 months and those who are breast feeding.
- g. History of autoimmune disease, immunosuppressive therapy, malignancy, or uncontrolled diabetes (HbA1c >10%).

Study treatment

The treatment phase will begin with a series of assessments designed to confirm the patients' continued eligibility. Subjects who continued to meet study inclusion criteria after the screening period were randomized to one of two groups:

- 1. HPTC
- 2. dHCAM

Interventions

Wound Preparation - Prior to application, wounds will be debrided to remove necrotic tissue and cleansed with a standard saline solution.

Application Protocol:

- a. HPTC Group: Participants will receive standard wound care plus application of HPTC
- b. dHCAM Group: Participants will receive standard wound care plus application of dHCAM

All participants will receive standard care measures, including:

- a. Regular repositioning to alleviate pressure.
- b. Nutritional support to address deficiencies.
- c. Management of comorbid conditions.

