Randomization and Blinding

Patients will be randomized 1:1 to the HPTC or dHCAM group using a computer-generated randomization sequence. Due to the nature of the interventions, blinding of participants and clinicians is not feasible. However, outcome assessors and data analysts will be blinded to group assignments.

Data Collection and Monitoring

- a. Baseline data: Demographics, medical history, ulcer characteristics.
- b. Weekly follow-ups: Wound measurements (photographic documentation), assess healing progress, record adverse events and patient-reported outcomes.
- c. End-of-Study Visit (Week 5): final wound assessment, collect patient feedback on treatment experience.
- d. Data entry and monitoring will be managed using an electronic data capture system.
- e. Regular monitoring will ensure adherence to the study protocol and address any compliance issues.

Statistical Analysis

Descriptive statistics for baseline characteristics. Statistical analysis was performed using SPSS version 26.0 (IBM Corp., Armonk, NY). Continuous variables were presented as mean \pm standard deviation or median (interquartile range) based on distribution normality assessed by Kolmogorov-Smirnov test. Categorical variables were presented as frequencies and percentages.

Between-group comparisons for continuous variables were performed using independent t-test or Mann-Whitney U test as appropriate. Chi-square test or Fisher's exact test was used for categorical variables. Time-to-event analysis was performed using Kaplan-Meier survival curves with log-rank test. Repeated measures ANOVA was used to analyse wound size changes over time.

Statistical significance was set at p<0.05. All analyses were performed on intention-to-treat basis with last observation carried forward for missing data.

Sample Size Calculation

Sample size calculation was based on expected difference in wound closure rates between groups. Assuming 85% closure rate in HPTC group versus 65% in dHACM group, with 80% power and 5% significance level, 38 patients per group were required. To account for 10% dropout rate, 40 patients per group were enrolled.

Study completion

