Patients will complete the study 6 weeks after the first treatment visit. In addition, if, patients whose study ulcer closes prior to the 6-week visit will be considered as having completed the study. Complete healing of the study ulcer is defined as 100% re-epithelialization without drainage. At any point during the treatment period, patients can refuse to participate or withdraw from the study without prejudice. If a patient withdraws from the study, their last available wound measurement will be carried forward and used to calculate change in wound size and their final outcome

Ethical Considerations

- i. Approval will be obtained from the Institutional Ethics Committee.
- ii. Adherence to the Declaration of Helsinki and Good Clinical Practice (GCP) guidelines.
- iii. Informed and written consent will be obtained from all participants.
- iv. Adverse events will be monitored and reported.
- v. Participants may withdraw at any time without penalty.
- vi. Dissemination of Results
- vii. Findings will be submitted to peer-reviewed journals and presented at relevant conferences.

Timeline

Recruitment: 1 months Intervention: 3 months

Data analysis and reporting: 1 months

Potential Implications

This study aims to provide direct comparative data on the efficacy of HPTC versus dHACM in the treatment of pressure sores. The findings could inform clinical decision-making and potentially lead to improved patient outcomes in wound care management of pressure sores.

References:

- 2. Berhane, C. C., Brantley, K., Williams, S., Sutton, E., & Kappy, C. (2019). An evaluation of dehydrated human amnion/chorion membrane allografts for pressure ulcer treatment: a case series. *Journal of Wound Care*, 28(Sup5), S4–S10. https://pubmed.ncbi.nlm.nih.gov/31067170/
- 3. Vecin, N. M., & Kirsner, R. S. (2023). Skin substitutes as treatment for chronic wounds: current and future directions. *Frontiers in Medicine*, 10, 1154567. https://www.ncbi.nlm.nih.gov/pmc/articles/PMC10498286/
- 4. Helicoll® Clinical Study Publications. [https://helicoll.com/clinical-studies/]
- 5. A Randomized Controlled Clinical Trial Comparing the Use of High-Purity Type I Collagen Matrix (HPTC) and Dehydrated Human Amnion/Chorion Membrane (dHACM) Allografts in the Management of Diabetic Foot Ulcers.

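### Wound size over time: repeated measures ANOVA is left open on scale, baseline, tested effect and sphericity, and LOCF is a separate weakness; a baseline-adjusted mixed model without LOCF is a cheap improvement

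*Combined protocol and SAP*

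**What the plan says.** The longitudinal plan is one sentence in Statistical Analysis: "Repeated measures ANOVA was used to analyse wound size changes over time". It serves secondary outcome b in Outcome Measures, "Wound Size Progression Over Time 7 weeks". The significance rule is "Statistical significance was set at p<0.05"; sidedness is not given.

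Missing data are covered twice. Statistical Analysis states "All analyses were performed on intention-to-treat basis with last observation carried forward for missing data". Study completion adds that for a patient who withdraws, "their last available wound measurement will be carried forward and used to calculate change in wound size and their final outcome".

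Two other entries matter. The inclusion criteria allow "Ulcer size between 5 cm² and 25 cm²". Data Collection and Monitoring gives the schedule as "Weekly follow-ups: Wound measurements (photographic documentation), assess healing progress" and the last visit as "End-of-Study Visit (Week 5): final wound assessment". Study Design instead has 6 weeks of intervention plus 1 week of follow-up, Study completion ends at 6 weeks, and the outcome itself is labelled 7 weeks.

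The plan does not state whether wound size means area or percent of baseline, whether baseline is a level of the time factor or a covariate, whether the group effect or the group-by-time interaction is tested, or whether sphericity is checked or corrected.

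**The concern.** Three separate matters meet in this analysis.

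1. **Sphericity.** The univariate group-by-time F test is valid only if all pairwise differences between visits have equal variance. Healing areas do not behave like that: adjacent weeks are highly correlated, and the spread collapses as ulcers close. Without a correction the test rejects too often.
2. **Baseline.** Entry area can vary five-fold (25/5 = 5). If raw area is analysed with baseline as one of the time levels, this between-patient spread stays in the error term of the group effect. A baseline-adjusted analysis removes it.
3. **LOCF.** An ulcer that is still open at withdrawal is frozen at its last size, and the frozen value is treated as observed. Participants and clinicians are not blinded, so withdrawal could differ between arms. The arm with more withdrawals would then look as if it heals more slowly.

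At stake is the reliability of one secondary outcome. The primary outcomes and the sample size do not use this model, although the LOCF rule applies to all analyses.

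**Working it through.** **Inputs from the documents.** 40 per arm; entry area 5-25 cm²; weekly measurements; alpha 0.05 (taken as two-sided); 10% dropout (Sample Size Calculation). Study Design also lists 20 per group beside 40 per arm; 40 is used here. The plan gives no power or error rate for this analysis, so there is no figure of its own to reproduce.

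**Assumptions.** The documents give no standard deviations or healing curves. Entry area is taken as uniform on 5-25 cm², and healing rates as lognormal between patients. Two families of curves were simulated, with 2,000 to 4,000 trials per setting:
- A: exponential healing, median rate 0.45 per week, log-SD 0.4-0.8, measurement error 12%, area below 0.5 cm² set to 0.
- B: linear-to-zero or exponential-type healing, log-SD 0.3-0.6, measurement error 10%.

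Monte Carlo error at 3,000 trials is √(0.05 × 0.95 / 3000) = 0.4 points near 5%, and √(0.5 × 0.5 / 3000) = 0.9 points near 50%.

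**Step 1: sphericity, no dropout, no treatment difference.** Simulated epsilon is 0.20-0.30 (1 would be sphericity). An approximate check by formula:
- Seven time points (weeks 0-6), 80 patients, two groups: nominal degrees of freedom are 7 − 1 = 6 and 6 × (80 − 2) = 468. The 5% critical value is F = 2.12.
- With epsilon 0.26, the effective degrees of freedom are 0.26 × 6 = 1.56 and 0.26 × 468 = 121.7. P(F(1.56, 121.7) > 2.12) = 13.6%.

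The simulations agree in size. False-positive rate of the uncorrected group-by-time test:

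| Outcome analysed | Uncorrected |
|---|---|
| Raw area, weeks 0-6 (curves B) | 11.8-12.5% |
| Raw area, weeks 0-7 (curves B) | 12.9-14.0% |
| Raw area, baseline included (log-SD 0.6) | 12.5% |
| Raw area, post-baseline only (log-SD 0.6) | 11.5% |
| Percent of baseline, baseline included (log-SD 0.6) | 11.0% |
| Percent of baseline, post-baseline only (log-SD 0.6) | 9.2% |

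The lowest result on any scale was about 8%. With Greenhouse-Geisser the rate is 4.2-5.4%, with the multivariate test 4.0-4.8%, and for the group main effect 4.7-5.4% (curves B). Baseline as a time level therefore does not inflate error.

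**Step 2: power, no dropout.** Curves A, log-SD 0.6, healing rate in one arm multiplied by 1.3 / 1.5 / 1.7:

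| Analysis | 1.3 | 1.5 | 1.7 |
|---|---|---|---|
| ANOVA group effect, raw area, baseline as a time level | 24% | 46% | 68% |
| ANCOVA of mean post-baseline area on baseline area | 42% | 74% | 93% |
| ANOVA group effect, post-baseline percent of baseline | 47% | 79% | 96% |

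Repeated runs at the 1.5-fold rate gave 46-49%, 74-77% and 79-84% for the three rows; the figures quoted elsewhere in this point are 49%, 76% and 84%. Curves B gave, for row 1 against row 2, 31% vs 64%, 22% vs 36%, 42% vs 82% and 28% vs 47%. The loss is specific to raw area with baseline inside the outcome.

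**Step 3: LOCF.** Curves B, linear healing, log-SD 0.4; closed ulcers stay at 0.

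Equal 10% dropout, power without and with dropout plus LOCF: ANOVA group effect 31% to 25%; ANCOVA on the post-baseline mean 64% to 50%; ANCOVA at the last visit 55% to 33%. Error of the corrected repeated-measures tests stays at 4.3-5.4%.

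Unequal dropout, no treatment difference. Expected withdrawals are 40 × 0.05 = 2 against 40 × 0.15 = 6, and 0 against 40 × 0.20 = 8. Each cell gives weeks 0-6 / weeks 0-7:

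| Test, with LOCF | 5% vs 15% | 0% vs 20% |
|---|---|---|
| Group-by-time, uncorrected | 16.7 / 17.3% | 28.4 / 27.3% |
| Group-by-time, Greenhouse-Geisser | 7.8 / 7.3% | 15.6 / 13.8% |
| Group-by-time, multivariate | 6.6 / 5.4% | 11.6 / 9.1% |
| Group effect, baseline as a time level | 6.5 / 7.1% | 10.5 / 10.9% |
| ANCOVA, post-baseline mean | 8.0 / 8.1% | 17.7 / 17.0% |
| ANCOVA, last visit | 11.7 / 12.4% | 37.0 / 39.3% |

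The last two rows show that LOCF harms a baseline-adjusted analysis as well. Changing the model while keeping LOCF would not cure it.

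**The case against.** The strongest reply is that the plan says much less than a critic might read into it. A reader might infer that the method analyses raw area, treats baseline as an outcome, uses an uncorrected F test, and forces the use of LOCF, so that it costs power and doubles false positives in itself. The documents do not support this:
- Raw area and baseline as a time level are not stated. Percentage reduction is a separate primary outcome, which makes raw area a natural reading of wound size. But Study completion speaks of change in wound size, so a baseline-relative scale is also open. On percent of baseline the ANOVA loses no power.
- No uncorrected test is named. A Greenhouse-Geisser or multivariate test restores about 5%, and the group main effect never loses it.
- LOCF is a rule for all analyses. Nothing says it was adopted because ANOVA needs complete rows. At equal 10% dropout the corrected tests hold their level.
- The outcome is secondary, and the mixed model itself was not simulated.

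All of this stands, and it limits the claim. It does not remove it. As written, the plan permits an uncorrected interaction test on raw area just as it permits a corrected test on percent of baseline, and the choice could be made after the data are seen. LOCF is stated, not inferred, and its cost does not depend on how the ANOVA sentence is read.

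**Conclusion.** The point holds in conditional form, as a recommended improvement to a secondary analysis.
- If the group-by-time test is uncorrected, its false-positive rate is about 8-13% depending on scale (up to 14% with eight time points), against about 5% with Greenhouse-Geisser.
- If raw area is analysed with baseline as a time level, the group effect has about 49% power against 76% for a baseline-adjusted analysis at a 1.5-fold healing rate. On percent of baseline (84%) there is no loss.
- LOCF costs power at equal 10% dropout. At 5% versus 15% it pushes most corrected tests to roughly 6-11% (single runs 5.4% to 12.4%), and further at 0% versus 20%.

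These sizes rest on assumed healing curves and a uniform spread of entry area. The advantage of baseline adjustment was measured with ANCOVA as a stand-in for the mixed model. The mean-over-weeks ANCOVA is also more powerful than a final-week comparison: on curves A, week-6 ANCOVA gave 37%, 65% and 85%. The direction was the same in every setting tried.

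**What to change.** 1. Reconcile the final visit (week 5, 6 or 7) across Outcome Measures, Study Design, Data Collection and Monitoring, and Study completion, and list the analysis weeks.
2. Replace the ANOVA sentence with a mixed model for repeated measures on weekly area from week 1 onward. Include treatment, week, treatment-by-week and baseline area, with unstructured covariance. Keep area at 0 after closure, and use no LOCF in the main analysis.
3. Report the adjusted difference at the reconciled final week with a 95% CI.
4. If repeated measures ANOVA is kept as a supporting analysis, state its scale, baseline handling and tested effect, and use a Greenhouse-Geisser correction.
5. Keep LOCF and one missing-not-at-random analysis as sensitivity analyses.

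The cost is SAP wording: no extra patients or visits are needed, and the named software has a mixed-model procedure. The downside is that the model assumes data are missing at random after withdrawal, which step 5 is there to probe. With six post-baseline weeks the covariance has 6 × 7 / 2 = 21 parameters for 80 patients, so a fallback structure should be named in case the fit does not converge.

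### Wound area reduction and six histology items are all primary at an unadjusted p<0.05 with no success rule; if any one counts, the false-positive chance is about 30% (independent tests) or 11% (correlation 0.9)

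*Combined protocol and SAP*

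**What the plan says.** The primary list under Outcome Measures has two entries: "Percentage Wound Area Reduction" and "Histopathological Parameters". The second has six numbered sub-items: vascular infiltration, neo-epithelialization, fibroblast activity, capillary density, inflammatory response and collagen deposition. No score combining them is defined.

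Statistical Analysis assigns tests by type of variable: t-test or Mann-Whitney for continuous data, chi-square or Fisher for categorical data. It mentions a Kolmogorov-Smirnov normality check, tied expressly to how continuous variables are summarised. It then states "Statistical significance was set at p<0.05". No section orders the primary outcomes, adjusts for their number, or says how many must succeed.

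The Sample Size Calculation does not identify a lead outcome. It rests on closure rates, and closure is listed as secondary: "Complete Wound Closure Rates (defined as 100% epithelialization".

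Two items needed for any repair are stated inconsistently.
- **End of study.** The secondary outcomes give "Wound Size Progression Over Time 7 weeks", and Study Design gives "6 weeks of intervention with follow-up for 1 week", which also totals 7. Data Collection and Monitoring places the final visit at Week 5, and Study completion places it at 6 weeks.
- **Group size.** "Sample Size: 80 patients (40 per arm" is followed directly by "Group A: 20 patients receiving HPTC treatment", with 20 for Group B as well.

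**The concern.** The plan does not define a positive trial. With seven primary results and one unadjusted threshold, a report could present a single significant histology item as success on a primary outcome, and on that reading the error rate is well above 5%. On the opposite reading, where all seven must be significant, the error rate is protected but the trial becomes hard to win. Nothing written stops the choice between these readings from being made once results are known. Blinding of assessors and analysts does not close this gap, because the rule can still be chosen after unblinding.

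**Working it through.** **The plan's own figure.** The plan states no family-wise error rate to reproduce. Its one calculated design figure is 38 per group for 85% versus 65% closure, 80% power and 5% level. With the pooled two-sided formula and mean rate 0.75:

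n = [1.960·√(2·0.75·0.25) + 0.842·√(0.85·0.15 + 0.65·0.35)]² / 0.20² = (1.200 + 0.501)² / 0.04 = 72.4, so 73 per group.

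One-sided, the same formula gives 57. Neither gives 38. Two-sided power at 38 per group is 52%. This defect is separate from the error-rate question and does not affect it.

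**Inputs for the error rate.** Each test uses 0.05 (Statistical Analysis). The number of tests is 1 + 6 = 7 if each histology item is tested, or 2 if histology is one score (Outcome Measures; the plan does not say which). The documents give no correlation ρ between test statistics, so a range is assumed.

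**Independent tests, any one counts.**
- Seven: 1 − 0.95⁷ = 30.2%.
- Two: 1 − 0.95² = 9.75%.

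**Correlated tests.** For k equally correlated normal statistics with c = 1.960:

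P(any) = 1 − ∫ [Φ((c − √ρ·u)/√(1−ρ)) − Φ((−c − √ρ·u)/√(1−ρ))]ᵏ φ(u) du

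**All seven required, 80% power each.** Joint power = ∫ [Φ((0.842 + √ρ·u)/√(1−ρ))]⁷ φ(u) du, which is 0.8⁷ = 21% at ρ = 0.

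| ρ | any of 7 | any of 2 | joint power, all 7 |
|---|---|---|---|
| 0 | 30.2% | 9.8% | 21% |
| 0.3 | 27.1% | 9.5% | 36% |
| 0.5 | 23.0% | 9.1% | 45% |
| 0.7 | 17.8% | 8.3% | 55% |
| 0.9 | 11.4% | 7.0% | 67% |
| 0.95 | 9.2% | 6.5% | not computed |

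**Sensitivity.**
- Histology items correlated 0.5 to 0.9 with each other and 0 to 0.3 with wound area: 14.8% to 24.7% over seven tests.
- Histology items yes/no and tested by Fisher's exact test, which is conservative. At 40 per group, with assumed event rates of 20% or 50%, the actual size per test is 0.028 or 0.033. With independence, 1 − 0.95·(1 − 0.028)⁶ = 20% and 1 − 0.95·(1 − 0.033)⁶ = 22%. At 20 per group the figure is 16% to 17%. Correlation would lower these further.

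**Effect of an adjustment.** At 0.05/7 = 0.00714 per test, seven independent tests give 1 − (1 − 0.00714)⁷ = 4.9%. The difference detectable with 80% power by a two-sided t-test (noncentral t) rises from 0.63 to 0.81 SD at 40 per group, and from 0.91 to 1.17 SD at 20.

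**Closure power.** Power = Φ[(difference − 1.960·√(2·p̄(1−p̄)/n)) / √((p₁(1−p₁) + p₂(1−p₂))/n)].
- 85% versus 65%, n = 40: Φ[(0.20 − 1.960·0.0968)/0.0942] = Φ(0.11) = 54%. At n = 20: 30%.
- If the planned 10% dropout all withdraw unhealed and are carried forward as unhealed, the rates become 0.9·85% = 76.5% and 0.9·65% = 58.5%. At n = 40: Φ[(0.18 − 1.960·0.1047)/0.1028] = Φ(−0.25) = 40%. At n = 20: 22%.

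**The case against.** The strongest reply is that no section says one significant result is enough. That is true. A reader might infer from the 30% figure that the plan adopts an any-one-wins rule; it adopts no rule at all, and the inflation exists only on that reading. What remains is that the plan leaves the reading open, and each available reading has a cost.

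A reader might also take 11% and 7% as floors. They are not: they require correlation 0.9, and at 0.95 the figures are 9.2% and 6.5%. The rates come close to 5% only near perfect correlation.

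A further tempting inference is that the wording on t-test or Mann-Whitney lets the analyst pick the more favourable p-value. No section permits that. The normality check, though attached only to presentation, is the natural guide to the test. Under assumed data with 65% to 85% of values at exactly 100% and the rest uniform from 20% to 95%, simulated Kolmogorov-Smirnov checks reject normality in about 90% of samples at 20 per group and over 99% at 40. The plan would then usually arrive at Mann-Whitney, so no extra error is claimed here for the choice of test.

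Nor is histology wholly without a test: the rules by variable type would cover it once its scale is known. The scale and time point are missing, and the data collection list names no tissue sampling, but that is a separate gap.

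Finally, a reader might infer that carrying the last observation forward makes dropout irrelevant to power. It preserves the number analysed, but a patient who withdraws unhealed counts as unhealed, so the rates and the difference shrink.

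**Conclusion.** The point stands and should be fixed before analysis. Seven results are primary at one unadjusted threshold, and the plan does not say which of them make the trial positive. If any one counts, the two-sided false-positive chance is about 30% with independent tests, 23% at correlation 0.5 and 11% at 0.9. With histology as one score it is 9.8% to 7.0% over correlation 0 to 0.9. These figures assume equal correlation and tests of exact 5% size; conservative exact tests on yes/no items would lower them. If all seven are required there is no inflation, but at an assumed 80% power each, joint power is 21% to 67% over the same correlations.

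The sample-size statement is wrong as written, but that is a separate defect and does not raise the false-positive rate.

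**What to change.** Make these changes before any unblinded analysis, with the registry and ethics record updated. The Sample Size Calculation speaks of patients as already enrolled, so the sponsor should state whether data by arm have been seen; if so, label the change post hoc.

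1. **One primary outcome.** Reconcile the end week across the four places listed above, then name percentage wound area reduction from baseline at that week as the single primary outcome, at two-sided 0.05 with one pre-named test. Mann-Whitney with tie correction is reasonable, because at the plan's expected closure rates many values would tie at 100%.
2. **Histology.** Make the six items secondary, each with a scale, time point and test, and test them as one Holm-adjusted family only if the primary is significant. Alternatively, keep all seven primary with Holm across them.
3. **Sample size (separate).** Reconcile 40 per arm with 20 per group and replace the 38-per-group claim. State closure power as about 54% at 40 per group (30% at 20) if 85% and 65% already count withdrawals as unhealed, falling to about 40% (22%) if the planned 10% dropout all withdraw unhealed. State that 80% power would need about 73 per group when those rates already count withdrawals.

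**Cost.** The multiplicity repair is wording only and needs no extra patients. Whether fixing a histology time point adds a procedure depends on sampling arrangements that the document does not describe. An isolated histology result could no longer be called a primary success. Holm across seven costs sensitivity at its strictest step: 0.63 to 0.81 SD at 40 per group by t-test. Mann-Whitney can also lose power to the t-test if unhealed ulcers do better in the arm with more closure. In one assumed simulation at 40 per group (85% versus 65% closure; unhealed values uniform 60–95% versus 20–95%), power was 66% against 85%.

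### Last observation carried forward is the only missing-data rule, so unequal withdrawal between arms can bias percentage wound area reduction, a primary outcome, and no planned analysis would show it

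*Combined protocol and SAP*

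**What the plan says.** Percentage wound area reduction is the first primary outcome under Outcome Measures. Two places set the handling of missing data, and they agree:

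- Statistical Analysis: "All analyses were performed on intention-to-treat basis with last observation carried forward for missing data".
- Study completion, for a patient who withdraws: "their last available wound measurement will be carried forward and used to calculate change in wound size and their final outcome".

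The analyses this touches are all in Statistical Analysis:

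- Group comparison: "Between-group comparisons for continuous variables were performed using independent t-test or Mann-Whitney U test as appropriate".
- Course over time: "Repeated measures ANOVA was used to analyse wound size changes over time".
- Closure: "Time-to-event analysis was performed using Kaplan-Meier survival curves with log-rank test". The treatment of withdrawals in this analysis is not stated.

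Early closure is handled separately: "patients whose study ulcer closes prior to the 6-week visit will be considered as having completed the study".

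No multiple imputation, likelihood-based, complete-case or worst-case analysis is named, and nothing provides for reporting withdrawals by arm, week or reason. Sample Size Calculation gives one dropout rate, 10%, without a split by arm. Wounds are measured weekly (Data Collection and Monitoring).

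**The concern.** The plan assumes 85% and 65% closure, so it expects ulcers to shrink a good deal during follow-up. A carried-forward value from an early week then understates the healing the patient would probably have reached. If one arm loses more patients, or loses them earlier, its mean reduction is pulled down further, even when the products work equally well.

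Unequal withdrawal is possible because "blinding of participants and clinicians is not feasible". Blinded assessors protect the measurement, not the decision to leave. Nothing in the documents says the arms will differ: both receive an active product plus the same standard care.

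The other planned analyses do not expose the problem. Repeated measures ANOVA falls under the same rule and uses the carried-forward values. Kaplan-Meier could avoid it for closure if withdrawals were censored, but it does not address area. Carry-forward could therefore create, inflate or hide a difference on a primary outcome without any planned analysis revealing it.

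**Working it through.** **Inputs from the plan.** 40 per arm; 10% dropout; 85% vs 65% closure, mean (85 + 65)/2 = 75%; weekly measurement; week 6 taken as the endpoint. The plan gives no figure for the effect of missing data, so there is none to reproduce. Going from 38 to 40 patients allows for only 1 − 38/40 = 5% dropout, so a 5% overall case is included.

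**Assumptions, not in the plan.** Withdrawal splits and timing, healing curves and SDs.

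**Step 1: the mechanism.** With no true effect, let P be the final mean reduction in both arms, d an arm's withdrawal share, t the withdrawal week and R(t) the mean reduction by then. The carried-forward mean is (1 − d)P + d·R(t), so

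false difference (A − B) = d_B[P − R(t_B)] − d_A[P − R(t_A)].

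- P = 80, linear healing R(t) = 80t/6, 5% vs 15%, all leaving at week 2: (0.15 − 0.05) × (80 − 26.67) = 5.3 points.
- Same, with a plateau curve R(t) = 80(1 − e^(−0.4t))/(1 − e^(−2.4)), so R(2) = 48.4: 0.10 × 31.6 = 3.2 points.
- P from 60 to 90 and both curves: 2.4 to 6.0 points.
- 10% in each arm, linear, week 4 vs week 1: 0.10 × (53.3 − 13.3) = 4.0 points.
- Same share and same week in both arms: 0.

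**Step 2: simulation.** 2,000 trials per setting, six weekly values, closure absorbing at 100%, closers unable to withdraw, withdrawal after weeks 1-4, linear and two decelerating healing shapes, all calibrated to 75% closure. Monte Carlo error is about 0.5-0.9 percentage points on rates near 5-20% and up to 0.1 points on bias. Values pile up at 100%, and a Kolmogorov-Smirnov test (Lilliefors form) rejected normality in at least one arm in all 200 trials checked per setting. The plan's phrase "based on distribution normality assessed by Kolmogorov-Smirnov test" formally governs data presentation; on its natural reading it also selects Mann-Whitney, so that test is shown.

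| Withdrawal, no true effect | False difference, points | Mann-Whitney false positives |
|---|---|---|
| 5% vs 15%, random | 4.7-5.1 linear; 2.8-3.5 decelerating | 12-15% |
| 5% vs 15%, slow healers leaving | 3.5-5.1 | 9-12% |
| 7.5% vs 12.5% | 1.5-2.5 | 5-7% |
| 2.5% vs 7.5% | 1.4-2.4 | 7-8% |
| 10% each, weeks 3-4 vs 1-2 | 2.3-3.5 | 4-6% |
| 10% vs 10%, same timing | about 0 | about 5% |
| 5% vs 15%, 20 per arm (Study Design also lists 20) | 2.9-4.9 | 8-10% |

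In the first row a t-test would give 14-24% false positives, and the group-by-week test of the repeated measures ANOVA on carried-forward values gives 11-22%.

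Hand check of the first row: the mean linear path is 19, 39, 58, 77, 90, 96. With withdrawal spread evenly over weeks 1-4 the gap is 96 − (19 + 39 + 58 + 77)/4 = 47.75, and 0.10 × 47.75 = 4.8 points. Repeating this row with separate code gave 2.4-4.8 points and 11-14%.

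**Step 3: the alternative.** A likelihood-based mixed model on the observed weekly values stayed within about 0.1 points, with 4-6% false positives, under random withdrawal. With slow healers leaving it was off by 0.1-0.3 points (complete-case 0.5-0.7). When withdrawal depended on the next, unseen area, it was off by 0.2-0.5 (carry-forward 3.5-4.9).

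**Step 4: with a true effect.** At 85% vs 65% closure the simulated true area difference is 2.5-3.9 points. Carry-forward reports 5.7-9.0 when the lower-closure arm loses 15% and the other 5%, and −0.9 to −0.1 when the split is reversed. The model gives 2.5-3.9 in both.

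**Step 5: closure.** With no true effect and 5% vs 15% random withdrawal, counting withdrawn patients as not closed gives a false difference of 6.8-7.8 points. Kaplan-Meier with censoring gives −0.7 to 0.4. If slow healers leave, these become 4.6-5.6 and −2.3 to −3.2.

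**The case against.** The strongest reply is that the harm needs a premise the plan does not supply. One dropout rate is given for both arms, both arms are actively treated, and at 10% vs 10% the bias is about zero and the test holds its level. The headline case is a threefold difference in withdrawal; at 7.5% vs 12.5% the Mann-Whitney rate is close to nominal. All of this stands and limits the claim. The split cannot be known in advance, though, which is why a check has to be specified beforehand.

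Timing alone shifts the estimate but does not clearly inflate Mann-Whitney. That also stands: it is a problem for the reported difference, not for that test's error rate.

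The healing curves are assumed to improve steadily. For a stalled ulcer carry-forward does little harm, and for a worsening one it flatters. So the size, and in an individual patient the direction, are uncertain. Carry-forward cannot be defended as conservative: its direction depends on which arm loses more patients and how their ulcers would have progressed.

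The plan could be read as deliberately targeting the last observed status. It never says so, and that reading would still make the comparison depend on when patients leave.

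Finally, the mixed model may go further than necessary. Most of the gain does come from dropping carry-forward, and complete-case analysis is nearly unbiased under random withdrawal. The simulated power at 10% withdrawal in each arm (37-41% for carry-forward with Mann-Whitney, 46-56% for the model) mixes several changes and should not be credited to one. The added noise is due to carry-forward: at 10% each its estimate has 1.8-2.1 times the model's SD, and a complete-case estimate also has about half the carry-forward SD.

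**Conclusion.** The concern holds. One rule covers every analysis, no second analysis is named, and the rule biases a primary outcome when the amount or timing of withdrawal differs by arm. Confidence is high that the problem exists and moderate about its size. At 5% vs 15% withdrawal the false difference is 2.8-5.1 points, as large as or larger than the true difference simulated for the planned closure rates; milder splits give 1.4-2.5 points with little or modest inflation of the Mann-Whitney error rate. These figures rest on assumed splits, curves and SDs. It should be corrected before the data are analysed.

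**What to change.** 1. Analyse percentage area reduction by a mixed model for repeated measures on the weekly values: treatment, week, treatment-by-week, baseline area and stage, with robust standard errors and no carry-forward for withdrawals. Take the contrast at one named week, once the passages that give 5, 6 and 7 weeks have been reconciled. The baseline covariates are optional: a precision gain of unknown size, not the correction of an error.
2. Enter ulcers that close early as 100% at later weeks, since the plan counts those patients as completers.
3. Keep carry-forward with the unadjusted test as a sensitivity analysis.
4. For closure, state that Kaplan-Meier censors withdrawals, or add multiple imputation from the weekly areas, as a sensitivity analysis.
5. Report withdrawals by arm, week and reason.

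The minimum version keeps the current test, names the mixed model as a sensitivity analysis and does item 5.

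The cost is SAP wording and a little more analysis, with no new visits or data. There are limits to state. The model assumes data are missing at random, and stronger dependence on unseen values would bias it more than shown above. Entering early closers as 100% assumes they stay closed. Censored Kaplan-Meier is not safe if slow healers leave (off by 2-3 points of closure).
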